# **Summary of Changes to the Protocol**

The previous version of this protocol (Version 3.0, 21 April 2016) was amended to create the current version (Version 4.0, 21 August 2017).

# **Protocol History**

Version and Date of Protocol	Comments
Version 1.0, 11 August 2015	Original version
Version 2.0, 23 September 2015	In response to regulatory feedback, the following changes were made:
	Clarification was added to dose escalation guidelines
	
 
Eligibility criterion 2 was modified to clarify that subjects in Part B must have confirmed advanced primary endometrial cancer (locally advanced and incurable endometrial cancer) that has been treated with surgery and/or radiation or is ineligible for such treatment in order to participate in this study
 

	
 
Dose modification and delay criteria were clarified and revised to include guidelines for hand foot syndrome and stomatitis
 

	Based on Investigator feedback, eligibility criteria were revised as follows:
	o Inclusion criterion 6a was changed from hemoglobin $\geq 8.0~g/dL$ to $\geq 9.0~g/dL$ for all subjects
	
 
Clarified that subjects receiving potassium, magnesium, or other supplementation for an otherwise controlled condition would be eligible for the study
 

	
 
Exclusion criterion 2 was updated to exclude subjects with uterine carcinosarcoma.
 

	Based on Investigator feedback, added that repetition of screening assessments that do not meet eligibility criteria in subjects who receive red blood cell transfusions or fluid replacement therapy will not require authorization from the medical monitor.
	• The timing of urine β-hCG testing was clarified.
	• Footnote "n" of Table 3-3 was revised to clarify PK sample collection for subjects in Part A.
Version 3.0, 21 April 2016	Due to sponsor decision, subjects with lymphomas will no longer be included in the study.
	Safety clinical laboratory assessments were clarified as follows:
	Coagulation parameter testing will be performed only at Screening
	
 
If blood urea nitrogen (BUN) cannot be collected, urea may be substituted.
 

	Clarified that assessments to be performed at the "end of cycle" may be performed up to 5 days before Day 1 of the subsequent cycle.
	Study drug dispensation and preparation instructions were revised to enable immediate dosing at study sites.

	Minor updates were made to the definitions of analysis sets and planned analyses for clarity and consistency.
Version 4.0, 21 August 2017	Current version

The following changes were made in the current version:

Change and Rationale	Affected Sections
Due to the study being transitioned from Vertex Pharmaceuticals Incorporated, Sponsor name changed to: EMD Serono Research & Development Institute, Inc., Billerica, MA, USA, Legal representative in the European countries: Merck KGaA, [name]	Cover page
EMD Serono internal study number: MS201926-0001	Cover page
Coordinating Investigator has been identified as per Merck KGaA requirement:  PPD  Tel: PPD  Fax: PPD	Cover Page
Medical Responsible has been identified as per Merck KGaA requirement:  PPD  Merck KGaA, Global Clinical Development, [name]  Tel: PPD  Fax:PPD	Cover page
Due to the changes in Sponsor, reference to "Vertex" changed to "the Sponsor"	Throughout protocol
Add EMD Serono compound code: M9831	Synopsis (Objectives, Investigational drug), Section 5
Due to the transition, Sponsor name changed from Vertex Pharmaceuticals Incorporated, Sponsor name changed to: EMD Serono Research & Development Institute	Section 9.5
The SAE reporting process was changed to comply with standard operating procedure	Section 13.1.2.3

Typographical and administrative changes were also made to improve the clarity of the document.

#### 2 PROTOCOL SYNOPSIS

**Title** An Open-Label, Phase I, First-in-Human Study of the Safety, Tolerability, and Pharmacokinetic/Pharmacodynamic Profile of VX-984 in Combination With Chemotherapy in Subjects With Advanced Solid Tumors

**Brief Title** 

A Study to Evaluate Safety, Tolerability, and Pharmacokinetic/Pharmacodynamic Profile of VX-984 in Combination With Chemotherapy

## Clinical Phase and **Clinical Study Type**

Phase I, first-in-human (FIH)

## **Objectives**

## PART A

#### **Primary**

- To evaluate the safety and tolerability of VX-984 (EMD Serono internal compound code: M9831) administered alone and in combination with pegylated liposomal doxorubicin (PLD) in subjects with advanced solid tumors
- To determine the maximum tolerated dose (MTD) of VX-984 in combination with PLD in subjects with advanced solid tumors.

#### Secondary

- To evaluate the pharmacokinetics (PK) of VX-984 when administered alone and in combination with PLD in subjects with advanced solid tumors
- To evaluate the PK of PLD when administered in combination with VX-984 in subjects with advanced solid tumors
- To evaluate preliminary antitumor activity of VX-984 in combination with PLD in subjects with advanced solid tumors.

## **Exploratory**

- To assess tumor response by tumor volume and tumor necrosis in subjects administered VX-984 in combination with PLD
- To assess correlations between prior treatment response and treatment outcome.

## **PART B**

## **Primary**

- To evaluate the safety and tolerability of VX-984 administered in combination with PLD in subjects with recurrent or metastatic endometrial cancer who have progressed on a prior platinum regimen
- To assess the overall response to VX-984 administered in combination with PLD in subjects with recurrent or metastatic endometrial cancer who have progressed on a prior platinum regimen.

## **Secondary**

- To assess progression free survival (PFS) in subjects with recurrent or metastatic endometrial cancer who have progressed on a prior platinum regimen administered VX-984 in combination with PLD
- To assess response duration (RD) in subjects with recurrent or metastatic endometrial cancer who have progressed on a prior platinum regimen administered VX-984 in combination with PLD
- To assess overall survival (OS) in subjects with recurrent or metastatic endometrial cancer who have progressed on a prior platinum regimen administered VX-984 in combination with PLD
- To assess clinical benefit in subjects with recurrent or metastatic endometrial cancer who have progressed on a prior platinum regimen administered VX-984 in combination with PLD as measured by complete response (CR), partial response (PR), or stable disease (SD) of 4 months or greater
- To evaluate the PK of VX-984 when administered in combination with PLD in subjects with recurrent or metastatic endometrial cancer who have progressed on a prior platinum regimen.

#### **Exploratory**

- CCI
- To assess tumor response by tumor volume and tumor necrosis in subjects with previously-treated endometrial cancer, administered VX-984 in combination with PLD
- To assess correlations between prior treatment response and treatment outcome
- · CCI

## Endpoints PART A

#### **Primary**

- Safety parameters, including adverse events (AEs), dose-limiting toxicities (DLTs), clinical laboratory values (serum chemistry and hematology), vital signs, echocardiogram, and electrocardiogram (ECG) assessments
- MTD of VX-984 in combination with PLD.

## **Secondary**

- Plasma PK parameter estimates of VX-984, administered alone and in combination with PLD, derived from plasma concentration-time data
- Plasma PK parameter estimates of PLD administered in combination with VX-984, derived from plasma concentration-time data
- Preliminary evidence of anti-tumor activity, including tumor response as evaluated by Response Criteria Evaluation RECIST 1.1 and tumor markers.

#### **Exploratory**

- CCI
- Tumor response as assessed by tumor volume and tumor necrosis using 3D computed tomography (CT) scans
- Tumor response as assessed by historical and on-treatment tumor growth dynamics
- CCI

## PART B

#### **Primary**

- Safety parameters, including AEs, clinical laboratory values (serum chemistry and hematology), vital signs, echocardiogram, and ECG assessments
- Objective response rate (ORR) as evaluated by CT scan per RECIST 1.1.

#### **Secondary**

- PFS
- RD as evaluated by CT scan and quantified by RECIST 1.1
- OS
- Clinical benefit (CR + PR + SD of at least 4 months)
- Plasma PK parameter estimates of VX-984 when administered in combination with PLD, derived from plasma concentration-time data.

## **Exploratory**

- CCI
- Tumor response as assessed by tumor volume and tumor necrosis using 3D CT scans
- Tumor response as assessed by historical and on-treatment tumor growth dynamics
- CC

## **Number of Subjects** Part A: approximately 50 subjects

Part B: approximately 40 subjects

## **Study Population**

At least 18 years of age, with tumors measurable by RECIST 1.1

Part A: male and female subjects with advanced solid tumors who have progressed through standard therapeutic options and for whom no standard therapy is available or PLD may be considered standard of care

Part B: female subjects with recurrent or metastatic endometrial cancer who have progressed on a prior platinum regimen

## **Investigational Drug**

Active substance: VX-984 (EMD Serono internal compound code: M9831)

Activity: DNA-dependent protein kinase (DNA-PK) inhibitor

Strength and Route of Administration: VX-984 suspension (in 0.5% methyl

cellulose) for oral administration

Dose: up to 3000 mg

## **Study Duration**

## Screening:

All subjects will have a Screening Visit within 14 days before the first dose of study drug.

## Treatment Periods:

Part A: Subjects in Part A will receive VX-984 as a single agent on Days -14 to -12 in a 14-day lead-in followed by VX-984 in combination with PLD for up to six 28-day cycles (PLD on Day 1 and VX-984 on Days 2 to 4). Subjects with tumors responding to treatment may continue on treatment past 6 cycles, with the agreement of the Investigator and medical monitor until disease progression, unacceptable toxicities, withdrawal of consent, or until exposure to PLD exceeds 550 mg/m^2.

Part B: Subjects in Part B will receive VX-984 in combination with PLD in 28-day cycles until disease progression, unacceptable toxicity, or withdrawal of consent.

## Follow-up:

All subjects will have a Safety Follow-up Visit 28  $(\pm 7)$  days after the last dose of study drug.

For Parts A and B, when possible, a follow-up CT scan will be performed  $5 (\pm 1)$  weeks after the end of therapy unless the subject had progressive disease at the time of treatment discontinuation or subject has initiated a new treatment in the interim. In Part B, for subjects without disease progression, long-term follow-up, including as indicated staging CT scans and/or follow-up communications, may continue for up to 1 year.

## **Study Design**

This is an open-label, multicenter, single-arm, FIH, dose-escalation study in subjects with solid tumors (Part A) followed by an expansion phase in subjects with recurrent or metastatic endometrial cancer who have progressed on a prior platinum regimen (Part B).

## Part A

Part A will be a dose escalation study to evaluate the safety, tolerability, and PK of VX-984 when administered in combination with PLD in subjects with

advanced solid tumors who have progressed through standard therapeutic options and for whom no standard therapy is available or PLD may be considered standard of care. This part will establish the MTD of VX-984 in combination with PLD.

## Starting dose and dosing schedule

For each VX-984 dose level tested, subjects will receive VX-984 once daily (qd) alone on Days -14 to -12 of a 14-day Lead-in Period. Following the single agent Lead-in Period, subjects will receive PLD on Day 1 and VX-984 qd on Days 2 to 4 of a 28-day cycle. The starting doses will be 120 mg qd of VX-984 and 40 mg/m² of PLD. The Lead-in Period will be required only if the dose of VX-984 is escalated beyond the highest dose of VX-984 previously tolerated in a Lead-in Period.

## Guidelines for dose escalation and determination of the MTD:

Three subjects will be enrolled at the starting dose of VX-984 (120 mg) and PLD (40 mg/m²). If the starting dose of VX-984 is tolerated alone in the 14-day Leadin Period and in combination with PLD through 1 cycle (28 days) without a DLT or CTCAE Grade 3 or worse toxicities in any of these 3 subjects and without a CTCAE Grade 2 toxicity in 2 subjects, the dose of VX-984 may be increased by up to 100% while holding the dose of PLD constant in a subsequent cohort of 3 subjects. Safety data, including AEs, laboratory values, and ECG results, obtained through the end of Cycle 1, as well as available PK data, will be assessed to determine the dose of VX-984 for the next cohort.

In this way, the dose of VX-984 will be escalated with 40 mg/m^2 of PLD in subsequent cohorts of 3 subjects until 1 subject has a treatment-related or possibly-related DLT or toxicity of CTCAE Grade 3 or worse; or 2 subjects (who may be in different cohorts) have a toxicity of CTCAE Grade 2.

Subsequent dose escalation will proceed depending on the toxicity as described:

- In the event of a treatment-related or possibly-related toxicity of CTCAE Grade 3 or worse in 1 subject (that is not considered a DLT), or treatment-related or possibly-related toxicity of CTCAE Grade 2 or worse (but not a DLT) in 2 subjects (who may be in different cohorts), the dose escalation will continue with a more conservative dose escalation (up to 50%). The dose of VX-984 will continue to be escalated in subsequent cohorts of 3 subjects until there is a DLT through the end of Cycle 1
- In the event of a DLT, an adaptive Bayesian logistic regression model (BLRM) will be used to determine the dose for the subsequent cohorts or determine if the current dose level should be expanded. At each predicted dose, 3 to 6 subjects will be enrolled in each cohort at the discretion of the sponsor and Investigators. If more than 3 subjects are enrolled, the first 3 subjects will receive VX-984 in the Lead-in Period and if no DLT is observed with VX-984 dosing then the additional subjects in the cohort will not have the Lead-in Period. The Lead-in Period will be required only if the dose of VX-984 is escalated beyond the highest dose of VX-984 previously tolerated in a Lead-in Period
- If 2 subjects in a previously untested dose level experience a DLT, enrollment to that cohort will stop, the BLRM will be updated and the next cohort will be opened at a lower dose level or an intermediate dose level that satisfies the escalation overdose control (EWOC) criteria. However, if 2 subjects in a new cohort at a previously tested dose level experience a DLT (e.g., a total of 8 subjects are tested on this dose level with 2 DLTs observed), further enrollment to that cohort will stop, the

BLRM will be updated with this new information and re-evaluation of the available safety, PK and PD data will occur. By incorporating information gained at the preceding dose levels, additional subjects may be enrolled into the current dose level only if the dose still meets the EWOC criteria and as agreed by the sponsor and Investigators.

Subjects will be considered as evaluable for dose determination if they have a DLT during Cycle 1 or the preceding Lead-in Period or meet the minimum treatment and safety evaluation requirements for the first cycle as outline in the protocol.

After completion of Cycle 1 of each cohort (3 to 6 subjects), available safety, PK, and efficacy information as well as recommendations from the Bayesian model will be used to determine the dose for the next cohort. The adaptive BLRM will be guided by the EWOC principle to control the risk of DLT in future subjects (see Statistical Analysis section for details).

After repeating the above steps, the dose escalation of VX-984 will continue with a constant dose of PLD at 40 mg/m² until MTD of VX-984 with PLD at 40 mg/m² is achieved. The maximum planned dose of VX-984 is 2000 mg; however, higher doses up to 3000 mg may be allowed depending on the observed safety, PK, and PD, and based on recommendation of the BLRM.

If a dose of VX-984 is not tolerated with PLD at 40 mg/m², then the VX-984 dose will be reduced by up to 50% with a constant dose of PLD at 40 mg/m² or the dose of PLD will be reduced by 25% (30 mg/m²) or lower with a constant dose of VX-984. These doses will be explored in subsequent cohorts at the discretion of the Investigators and sponsor until the MTD is established with PLD at 30 mg/m² or lower. If daily dosing of VX-984 for 3 days after PLD is not tolerated during initial dose escalation, less frequent dosing of VX-984 may be explored in subsequent cohorts.

#### Treatment duration and disease assessments:

At all dose levels of VX-984, subjects will complete a total of up to six 28-day cycles of VX-984 and PLD combination therapy. Subjects with tumors responding to treatment may continue on treatment past 6 cycles with the agreement of the Investigator and medical monitor until disease progression, unacceptable toxicity, or withdrawal of consent. CT scans will be performed at the end of every 2 cycles (see Table 3-3). If there is evidence of progressive disease as determined using RECIST 1.1, the subject's treatment will be discontinued. In addition, transthoracic echocardiograms will be performed at baseline and at the end of every 2 cycles (see Table 3-3). After 6 cycles, CT scans will be performed at the end of every 2 to 3 cycles (see Table 3-3).

#### Part B

Part B will be an expanded cohort study to confirm the safety, tolerability, PK, and potential anti-tumor activity of VX-984 in combination with PLD in female subjects with recurrent or metastatic endometrial cancer who have progressed on a prior platinum regimen.

During each cycle, subjects will be administered PLD on Day 1, and VX-984 will be dosed on Days 2 to 4 of a 28-day cycle unless in Part A the number of days was decreased due to tolerability. Approximately 40 subjects will receive VX-984 with PLD at the MTD or lower, as determined during the dose escalation phase.

Subjects will continue to receive treatment until disease progression, unacceptable toxicities, or withdrawal of consent. Subjects will be evaluated by CT scans at the end of every 2 cycles for the first 6 cycles and every 2 to 3 cycles thereafter (see Table 3-3). If there is evidence of progressive disease as determined using RECIST 1.1, treatment will be discontinued. In addition, subjects will be

evaluated by transthoracic echocardiogram at baseline and at the end of every 2 cycles (see Table 3-3).

# Pharmacokinetic Assessments

## Part A:

Blood samples for measurement of VX-984 PK (in plasma) will be collected during the Lead-in Period Days -12 to -11 and during Cycle 1 on Day 2 and on Days 4 to 5.

Urine samples for measurement of VX-984 PK will be collected during the Leadin Period on Days -12 to -11.

Blood samples for measurement of PLD PK (in plasma) will be collected at Cycle 1 on Days 1, 2, 4, and 5.

## Part B:

Blood samples for measurement of VX-984 PK (in plasma) will be collected during Cycle 1 on Day 4.

Blood sample for measurement of PLD PK (in plasma) will be collected during Cycle 1 on Day 4.

PK sampling may be conducted on Day 2 or Day 3 if subjects are unable to come to the clinic for PK sampling on Day 4.

These PK samples will be required in a minimum of 20 subjects. VX-984 dose will be administered in the clinic on the day of PK sampling.

## **Efficacy Assessments**

CT scans will be performed at Screening and at the end of every 2 cycles for the first 6 cycles and every 2 to 3 cycles thereafter, and at 5 ( $\pm$  1) weeks after the last dose of study drug (excluding subjects with progressive disease on previous CT scan) (see Table 3-3). For subjects with bony metastases, bone scans will be performed every 4 to 6 cycles or more frequently if clinically indicated.

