Concomitant medications		Continuous from signing of ICF through Safety Follow-up Visit						X	
AEs		Continuous from signing of ICF through Safety Follow-up Visit						X	
Study Drug Administration									
VX-984 m		X	X	X					
PLD	X								
Pharmacokinetic Assessments									

<sup>a Follow-up will include a Safety Follow-up Visit 28 (± 7) days after the last dose of study drug and a radiologic Follow-up Visit 5 (±1) weeks after the last cycle of chemotherapy, and survival follow-up assessment at the last subject last visit. In Part B, for subjects without disease progression, long-term follow-up, including as indicated staging CT scans and/or follow-up communications, may continue for up to 1 year. See Section 8.1.4 for additional details.

b Cycle 1 only.

<sup>c Day 2 visit is required for Part A only.

d Symptom-directed physical examinations will be performed as clinically indicated in the Investigator's judgment.

Table 3-3 Study VX15-	able 3-3 Study VX15-984-001: VX-984 and PLD Combination Therapy and Follow-up (Parts A and B)									
Event/Assessment	Day 1	Day 2	Day 3	Day 4	Day 5	Day 8	Day 15	Follo	w-up a	
During Each Cycle								28 days	5 weeks	
(Except as Noted)								(± 7 days)	(± 1 week)	
Part A VX-984 (Plasma PK collection)		X n		X n	X n					
Part A PLD (Plasma PK collection)	Xº	Xº		Xº	Xº					
Part B VX-984 (Plasma PK collection)				$X^p$						

<sup>e CT scan of chest, abdomen, and pelvis should be performed, in addition to CT scan of other body areas, as clinically indicated.

<sup>f End of cycle assessments may be performed up to 5 days before Day 1 of subsequent cycle.

<sup>g Assessment includes tumor staging (I to IV) and Tumor-Node-Metastasis.

h For all subjects with prostate cancer or for subjects with other malignancies in whom bony metastases have been previously documented or are highly suspected; or if clinically indicated.

Vital signs will be measured on Day 1 up to 60 minutes before administration of PLD and on Day 2 up to 60 minutes before administration of VX-984 and at 2 (± 1) hours after administration of VX-984.

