## 8.1.2.1.4 Treatment Duration and Disease Assessments

At all dose levels of VX-984, subjects will complete a total of up to six 28-day cycles of VX-984 and PLD combination therapy. Subjects with tumors responding to treatment may continue treatment past 6 cycles with the agreement of the Investigator and medical monitor until disease progression, unacceptable toxicity, withdrawal of consent, or until exposure to PLD exceeds 550 mg/m^2. Staging CT scans will be performed at the end of every 2 cycles (see Table 3-3). If there is evidence of progressive disease as determined using RECIST 1.1, the subject's treatment will be discontinued. In addition, transthoracic echocardiograms will be performed at baseline and at the end of every 2 cycles (see Table 3-3). After 6 cycles, CT scans will be performed at the end of every 2 to 3 cycles (see Table 3-3).

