# 8.1.2.1.7 Subject Evaluability

All subjects who meet the eligibility criteria and receive at least 1 dose of VX-984 will be evaluable for safety.

In order for subjects to be evaluable for dose escalation decisions:

- Subject must receive PLD on Day 1 and receive all 3 doses of VX-984 within 5 days (Days 2 to 6) with the first dose of VX-984 on Day 2; or
- The subject must have had a DLT during Cycle 1.

Subjects who do not fulfill at least 1 of the 2 above criteria will not be evaluable for dose escalation decisions and will be replaced.

In the event of a Grade 3 or higher elevation in ALT or AST, follow-up laboratory assessments should be performed every 48 to 72 hours until reduced to Grade 2 or lower.

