# 8.1.4 Follow-up (Parts A and B)

All subjects, regardless of reason for discontinuation, will have a Safety Follow-up Visit  $28 (\pm 7)$  days following the last dose of study drug, during which the procedures listed in Table 3-3 will be completed. In addition, all subjects who receive all scheduled study drug doses through Cycle 1, have not had evidence of disease progression, and have not initiated

cancer therapy outside of the study protocol will have radiologic follow-up 5 weeks  $(\pm 1 \text{ week})$  after the last cycle of chemotherapy.

A survival follow-up assessment will be performed for all subjects at the last subject last visit for that part. For the survival follow-up assessment, every subject who is not known to have died during the course of the study will be called to ascertain whether the subject is alive, if the subject has initiated another therapy, or if the subject died. If the subject has initiated another therapy or died, the date of initiation of the other therapy or date of death will be confirmed.

Subjects in Part B who complete at least 6 cycles of treatment, discontinue for reasons other than disease progression, and do not have disease progression on the radiologic follow-up visit will be followed by staging CT scan (if possible) approximately every 8 weeks until disease progression, the subject starts a new line of therapy, the subject dies, the study closes, or the subject is at least 12 months from end of treatment, whichever comes first.

Finally, for Part B, regardless of disease progression or initiation of new line of therapy, subjects may be followed by telephone, electronic, or mail communication, or in person, every 3 months for up to 1 year or until the subject is lost to follow-up or dies, whichever occurs first

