14.1 Analysis of Best Overall Response

Analysis Set: FAS/SAF

The best overall response (BOR) will be defined as the best response per RECIST 1.1 across all time points until determination of PD, using the Investigator reported overall response per time point and excluding assessments after further anticancer therapy Clinical deterioration will not be considered as documented disease progression.

Tumor assessments are based on local evaluations by the Investigator according to RECIST 1.1 criteria. Local evaluations of target, non-target and new lesions are used to assess BOR. The date of the overall response assessment is the earliest date for imaging of target, non-target and new lesions of images taken at that response assessment.

BOR will be defined as the best response across all time points (for example, a subject who has SD at the first assessment, PR at the second assessment, and PD at the last assessment has a BOR of PR). The order to obtain the BOR is the following: CR, PR, SD, PD and NE.

When SD is believed to be the best response, it must also meet the protocol-specified minimum 6 weeks from first day of treatment. If the minimum time is not met, the subject's BOR depends on the subsequent assessments. For example, a subject who has SD at the first assessment, PD at

the second assessment and does not meet the minimum duration for SD, will have a BOR of PD. The same subject lost to follow-up after the first SD assessment would be considered NE for BOR.

If a subject has missing baseline tumor assessment and/or no tumor assessment on-treatment, BOR will be NE.

The confirmed BOR will be also analyzed. In this case, CR and PR need to be confirmed at a subsequent assessment, at least 4 weeks after initial overall response assessment of CR/PR. Confirmed BOR will be derived as described in RECIST 1.1 guidance, see Table 5 below.

Both confirmed and unconfirmed BOR will be summarized by tabulating the number and percentage of subjects with CR, PR, SD, PD or NE as BOR. The table will also include the objective response rate (ORR), disease control rate (DCR) and the corresponding 90% Clopper-Pearson confidence intervals (Clopper & Pearson, 1934). The ORR will be defined as the rate of subjects who achieve either a CR or PR. The DCR will be defined as the rate of subjects who achieve either a CR, PR or SD.

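### The post-treatment CT has no single reference date; timed from the last dose, it comes too early to confirm a response first seen on a CT that closes the last dosed cycle

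*Protocol*

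**What the plan says.** The protocol describes one post-treatment CT, 5 (±1) weeks out, but counts those weeks from different points:

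- Synopsis, Efficacy Assessments: "weeks after the last dose of study drug (excluding subjects with progressive disease on previous CT scan". This sentence refers the reader to Table 3-3.
- Synopsis, Follow-up: "weeks after the end of therapy unless the subject had progressive disease at the time of treatment discontinuation". The scan is to be done when possible, and the end of therapy is not defined.
- Table 3-3, footnote a: "weeks after the last cycle of chemotherapy, and survival follow-up assessment at the last subject last visit". Figure 8-1, note d, uses the same reference point, and Section 8.1.4 places the scan "after the last cycle of chemotherapy". None of the three says whether the start or the end of the cycle is meant.

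On the dosing schedule, "subjects will receive PLD on Day 1 and VX-984 qd on Days 2 to 4 of a 28-day cycle". For Part A, Section 8.1.2.1.4 says "Staging CT scans will be performed at the end of every 2 cycles", and Table 3-3, footnote f, lets end-of-cycle assessments be done up to 5 days before the next Day 1.

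SAP 14.1 reports best overall response (BOR) both unconfirmed and confirmed, each with an objective response rate (ORR), a disease control rate (DCR) and 90% Clopper-Pearson intervals. For the confirmed version, "CR and PR need to be confirmed at a subsequent assessment, at least 4 weeks after initial overall response assessment of CR/PR".

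**The concern.** In each cycle, dosing is over by Day 4 and the staging CT comes at the end. A follow-up scan timed from the last dose therefore starts its clock more than three weeks before one timed from the end of the cycle. That difference decides whether the scan can meet the SAP's confirmation interval.

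Part A is planned for up to six cycles. Going further needs the agreement of the Investigator and the medical monitor. For a subject whose CR or PR first appears at the end of Cycle 6, or at the end of Cycle 2 or 4 with no further dosing, the follow-up CT is the only remaining scan on the Part A schedule. The roughly 8-weekly CT follow-up in Section 8.1.4 is for Part B, which the SAP says will not be pursued. At stake is the confirmed ORR, one of the planned summaries for the Part A secondary objective on anti-tumor activity. Two subjects with the same disease course could be classified differently because their sites used different passages.

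**Working it through.** The plan gives no figure to reproduce, so this is day arithmetic on its own windows. Days are counted from Day 1 of the last dosed cycle, and no cycle delay is assumed.

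**Inputs**

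- Last dose: Day 4 (synopsis and Section 8.1.2.1.1). Sensitivity cases: Day 6, because Section 8.1.2.1.7 accepts subjects who "receive all 3 doses of VX-984 within 5 days (Days 2 to 6"; and Day 1, if only PLD was given.
- End-of-cycle CT: the next Day 1 is Day 29, so 5 days earlier is Day 24. The window is Day 24 to 28, or Day 29 if the scan is done on the next Day 1.
- Follow-up CT: 5 (±1) weeks = 28 to 42 days after the reference point.
- Minimum interval for confirmation: 4 weeks = 28 days (SAP 14.1).

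**Formulas**

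- Shortest gap = (reference day + 28) − latest day of end-of-cycle CT
- Longest gap = (reference day + 42) − earliest day of end-of-cycle CT

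**Final CT closes the last dosed cycle**

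| Reference point | Follow-up CT | Gap, CT on Day 24–28 | Gap, Day 29 also allowed |
|---|---|---|---|
| Last dose, Day 4 | Day 32–46 | 32−28 = 4 to 46−24 = 22 | 3 to 22 |
| Last dose, Day 6 | Day 34–48 | 6 to 24 | 5 to 24 |
| Last dose PLD only, Day 1 | Day 29–43 | 1 to 19 | 0 to 19 |
| Start of last cycle, Day 1 | Day 29–43 | 1 to 19 | 0 to 19 |
| End of last cycle, Day 28 | Day 56–70 | 56−28 = 28 to 70−24 = 46 | 27 to 46 |

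At nominal timing (scan on Day 28, follow-up at 5 weeks) the gap is 4 + 35 − 28 = 11 days from the last dose and 28 + 35 − 28 = 35 days from the cycle end.

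A scan on Day 24 to 28 can be confirmed on Day 52 to 56 at the earliest. The last-dose window closes on Day 46 (Day 48 for a Day 6 dose), so no date inside it qualifies. The cycle-end window qualifies except in one corner: a Day 29 scan followed by the earliest possible follow-up, at 27 days.

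**Last dose given one cycle after the last scanned cycle** (for example, scan at the end of Cycle 2 and stopping after dosing in Cycle 3), timed from the last dose:

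- VX-984 given: 28 + 4 = Day 32, so follow-up on Day 60 to 74. Gap 32 to 50 days (31 to 50 with a Day 29 scan).
- PLD only: 28 + 1 = Day 29, so follow-up on Day 57 to 71. Gap 29 to 47 days (28 to 47 with a Day 29 scan).

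Both meet the minimum, so these subjects are not affected.

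**Effect per subject.** With about 50 treated subjects in the denominator (the planned Part A size), each unconfirmed response lowers the overall confirmed ORR by 1/50 = 2 percentage points.

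**The case against.** The strongest reply is that the last-dose wording is one synopsis sentence, and that it defers to Table 3-3. The table, the design figure and Section 8.1.4 agree with each other on the last cycle. Sites would probably follow those. This makes last-dose timing less likely but does not settle the matter. The last cycle could mean its start, which gives 1 to 19 days, and only the end-of-cycle reading works.

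A reader might infer that under last-dose timing every response first seen on the final on-treatment CT is beyond confirmation. The documents do not support that:

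- Subjects dosed in a further unscanned cycle have a long enough gap, as shown above.
- Part A responders may continue past Cycle 6 and be rescanned on treatment.
- SAP Section 9 includes unscheduled assessments in the efficacy analyses, and the footnote to the SAP's confirmed-BOR table lets a later scan that is not the next one confirm.
- Section 8.1.3 keeps subjects who stop for a non-reversible or life-threatening DLT in follow-up until documented progression, although it names no CT and no schedule.

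A reader might also infer that the SAP's table turns such a subject into SD. It has no row for a second response seen before 4 weeks. The text of SAP 14.1 denies confirmation, while the PR-then-PR row, read alone, gives PR. SD is an inference.

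It also stands that Part A efficacy is a secondary and preliminary objective without a power calculation, that unconfirmed BOR, ORR and DCR are reported alongside, and that the synopsis asks for the follow-up CT only when possible. These points limit the weight of the problem without removing it.

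**Conclusion.** The point holds in a limited form. The reference dates conflict, and the choice between them matters when the final on-treatment CT closes the last dosed cycle, as when a subject stops after Cycle 2, 4 or 6. In that case last-dose timing gives 4 to 22 days (1 to 19 if the last dose was PLD on Day 1), against a required 28. Cycle-end timing gives 28 to 46 days. In Part A no later CT is explicitly scheduled, so only an unscheduled scan or continued treatment could confirm a CR or PR first seen on that final CT. Confirmed BOR and ORR would be biased downward and would vary with the passage a site follows.

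This assumes no cycle delays, end-of-cycle CTs on Day 24 to 28, and an analysis that applies the 4-week rule as written in the SAP text. How many subjects are affected cannot be derived from the documents. The point should be corrected, but it does not threaten the primary safety and MTD objectives.

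**What to change.** Reconcile the synopsis (Follow-up and Efficacy Assessments), Table 3-3 footnote a, Figure 8-1 note d and Section 8.1.4 to one defined reference date: 5 (±1) weeks after the end (Day 28) of the last cycle started. Add that, if the previous CT was the first to show CR or PR, the follow-up CT is done at least 28 days after it. That clause also covers the 27-day corner case. The clause alone would not be enough, because the last-dose window closes before 28 days have passed. A sentence in SAP 14.1 on how to classify a second response seen before 4 weeks would close the gap in its table.

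The protocol change is to wording only and adds no scan. Its cost is timing: Day 28 − Day 4 = 24 days, so the CT comes about 3.5 weeks later than under last-dose timing. Some subjects may start new therapy first, and SAP 14.1 excludes assessments made after further anticancer therapy from BOR. If that is a concern, the later date can be limited to subjects whose last CT was the first to show CR or PR.
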